## 12.4 Reporting of other events

### 12.4.1 Overdose

An overdose is defined as a subject receiving a dose of IMP in excess of that specified in this protocol.

The term overdose must be documented on the AE form of the eCRF. In addition, AEs originating from overdose must be documented on a separate line. If the AE originating from overdose is serious expedited reporting is required (see Section 11.2.2.1).

In the event of an overdose, the patient should be monitored and treated symptomatically, and supportive measures instituted to the discretion of the investigator

### 12.4.2 Medication error

Medication error refers to any unintentional error in the dispensing or administration of a medicinal product while in the control of the (sub)investigator or subject. Broadly, medication errors fall into four categories: wrong medication, wrong dose (including strength, form, concentration, and amount), wrong route of administration, or wrong subject.

The medication error specifying the category of error (see definitions above) must be documented on the AE form of the eCRF. In addition, AEs originating from a medication error must be documented on a separate line. If the AE originating from medication error is serious expedited reporting is required (see Section 12.2.2.1).

### **12.4.3 Misuse**

Misuse refers to situations where the medicinal product is intentionally and inappropriately used not in accordance with the protocol.

The term misuse must be documented on the AE form of the eCRF. In addition, AEs originating from misuse must be documented on a separate line. If the AE originating from misuse is serious expedited reporting is required (see Section [12.2.2.1](#)).

### **12.4.4 Abuse**

Abuse relates to the sporadic or persistent, intentional excessive use of an IMP which is accompanied by harmful physical or psychological effects.

The term abuse must be documented on the AE form of the eCRF. In addition, AEs originating from abuse must be documented on a separate line. If the AE originating from abuse is serious expedited reporting is required (see Section [12.2.2.1](#)).

### **12.4.5 Aggravation of condition**

Any clinically significant aggravation/exacerbation/worsening of any medical condition(s), compared to baseline, must be reported as an AE. If the AE originating from aggravation of condition is serious expedited reporting is required (see Section [12.2.2.1](#)).

### **12.4.6 Lack of efficacy**

Not applicable.

## **12.5 Follow-up for final outcome of adverse events**

During the trial, the investigator should follow up for final outcome on all AEs (including SAEs). Once a subject leaves the clinical trial, the investigator should follow up on the outcome of all non-serious AEs classified as of possible/probable related to the investigational product for 8 weeks after last treatment for brodalumab or for 2 weeks after last treatment for fumaric acid esters, or until the final outcome is determined, whichever comes first. SAEs must be followed up until a final outcome has been established, i.e. the follow-up may continue beyond the end of the clinical trial. For SAEs which have stabilised and cannot be expected to recover during trial or safety follow-up periods, for example chronic illnesses, the final outcome should be considered recovered and a statement that the SAE has stabilised should be added to the narrative in the SAE form. Please note that the event should not be reported as 'recovered' in the eCRF and on the SAE form.

## 12.6 Handling of an urgent safety measure

An urgent safety measure is a measure taken to implement an action/protocol deviation under an emergency. This is defined within the EU Directive 2001/20/EC as “...*the occurrence of any new event relating to the conduct of the trial or the development of the investigational medicinal product where that new event is likely to affect the safety of the subjects, the sponsor and the investigator shall take appropriate urgent safety measures to protect the subjects against any immediate hazard.*” (EU 2001/20/EC, article 10).

If the investigator becomes aware of information that necessitates an immediate change in the clinical trial procedure or a temporary halt to the clinical trial in order to protect clinical trial subjects from any immediate hazard to their health and safety, the investigator can do so without prior approval from LEO, regulatory authority(ies), or IEC(s).

The investigator must immediately inform LEO - by contacting the clinical project manager or medical expert - of this change in the clinical trial procedure or of the temporary halt providing full details of the information and the decision making process leading to the implementation of the urgent safety measure.

LEO must act immediately upon receipt of the urgent safety measure notification in accordance with the internal procedures, which are based on the EU guideline.

## 13 Statistical methods

### 13.1 Sample size

The effect on psoriasis symptoms of subcutaneous injections of brodalumab will be compared to oral administration of fumaric acid esters in subjects with moderate to severe plaque psoriasis who are naïve to systemic treatment.

Formally, this will be formulated by testing the null hypotheses of equality of proportion of PASI 75 response and sPGA (0 or 1) success to treatment with brodalumab compared with treatment with fumaric acid esters; against the alternative hypothesis that the two proportions differ.

The sample size is determined using Fisher's exact test for the two independent proportions under the assumption of a two-sided test of size 5%. Based on experience from previous trials with brodalumab and fumaric acid esters in subjects with moderate to severe psoriasis, conservative estimates for the proportion of PASI 75 responders of 80% for brodalumab and between 50% and 70% for fumaric acid esters ([Nast et al. 2012](#)) are used in the sample size calculation (using Proc Power in SAS version 9.4). Assuming a dropout rate of 50% for

fumaric acid esters, a PASI 75 response rate combined with NRI will correspond to a total rate of responders of 25%. A dropout rate of less than 40% with brodalumab, a PASI 75 response rate will correspond to a total rate of responders of 48%.

For sPGA, the expected rate of sPGA success is 37.4% with fumaric acid esters ([Mrowietz and Szepietowski et al. 2017](#)), while varying rates above 60% has been seen in the previous brodalumab trials.

An overview of the estimated power within the given spread of response rates, is presented in [Panel 13](#).

**Panel 13 Estimated power by sample size and response rate (number of subjects per group)**

	PASI 75 Fumaric acid esters response rate = 50% (total response rate = 25%)	PASI 75 Fumaric acid esters response rate = 60% (total response rate = 30%)	PASI 75 Fumaric acid esters response rate = 70% (total response rate = 35%)	sPGA success Fumaric acid esters response rate = 37.4%
N = 91	0.873	0.652	0.372	0.833
N = 102	0.910	0.708	0.416	0.876
N = 118	0.947	0.776	0.476	0.921
N = 144	0.978	0.858	0.566	0.963

Assuming independence between PASI 75 and sPGA the power to show superiority of brodalumab compared to fumaric acid esters will be  $0.91 \times 0.876 = 80\%$  with 102 subjects in each treatment arm.

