### Brodalumab efficacy:

The efficacy of brodalumab for the treatment of psoriasis has been confirmed in 3 pivotal phase 3 placebo-controlled clinical trials, in which 2 of the trials also included an ustekinumab comparator arm. The pivotal trials enrolled subjects of 18 to 75 years of age with stable moderate to severe plaque psoriasis diagnosed at least 6 months before the first dose of investigational medicinal product (IMP). At baseline, the enrolled subjects had plaque type psoriasis with Psoriasis Area and Severity Index (PASI) score of at least 12, static Physician's Global Assessment (sPGA) score of at least 3, and at least 10% body surface area (BSA) involvement. In all 3 trials, brodalumab was superior to placebo ( $p < 0.001$ ) for the co-primary endpoints (PASI 75 and sPGA of 0 or 1) as well as the secondary endpoints at Week 12 (PASI 100, sPGA of 0, and PSI).

At Week 12, brodalumab 210 mg treated patients achieved response rates of 86% for PASI 75, 80% for sPGA0/1, and 44% for PASI 100 (AMAGINE-2 trial, EU summary of product characteristics (SmPC)).

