### 13.3.5 Analysis of primary endpoint

The co-primary endpoints PASI 75 and sPGA (0 or 1) at Week 24 (end of treatment visit) will be evaluated on the FAS.

Estimates and 95% confidence intervals (CI) for the response rates and treatment differences will be presented. The differences in response rates between treatment groups will be analysed using the Cochran-Mantel-Haenszel test with stratification by weight group ( $\geq 100$  kg or  $< 100$  kg). The null hypotheses of no difference in response rates between brodalumab and fumaric acid esters will be tested against the two-sided alternative that there is a difference on a 5% level. Subjects who drop-out of the trial before Week 24 (end of treatment visit) will be regarded as non-responders. A sensitivity analysis will be made where ineligible subjects randomised in error into the trial are excluded from the analysis.

As supportive analyses for the co-primary endpoints, a logistic regression model with baseline PASI or sPGA and weight group will be performed, and further, the mixed model for repeated measurements (MMRM) for PASI described below will be used to predict PASI 75 for subjects without assessments at Week 24 for an additional Cochran-Mantel-Haenszel analysis. Finally, subjects who drop-out of the trial before Week 24 will be LOCF imputed and analysed using the Cochran-Mantel-Haenszel test.

The trial is considered a success if superiority is confirmed for both primary endpoints.

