### **13.3.11 Handling of missing values**

Missing data for categorical endpoints will be imputed with non-responder imputation. Missing data for continuous endpoints will be dealt with by a mixed model for repeated measurements.

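### The stated 80% joint power combines a PASI 75 power taken after dropout with an sPGA power that has no dropout step; if the sPGA rates are completer rates, the planning values give about 68%

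*Combined protocol and SAP*

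**What the plan says.** Section 13.1 plans on Fisher's exact test, two-sided at 5%. For PASI 75 it starts from 80% on brodalumab and 50% to 70% on fumaric acid esters, then discounts for dropout. At 50% dropout in the comparator arm, "a PASI 75 response rate combined with NRI will correspond to a total rate of responders of 25" per cent. The brodalumab arm is handled thus: "A dropout rate of less than 40% with brodalumab, a PASI 75 response rate will correspond to a total rate of responders of 48" per cent.

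The sPGA 0/1 rates get no such step. The text says "For sPGA, the expected rate of sPGA success is 37.4% with fumaric acid esters" and, for brodalumab, that "varying rates above 60% has been seen in the previous brodalumab trials". Panel 13 follows the same pattern: each PASI 75 column carries a total response rate, and the sPGA column does not.

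Below Panel 13 the two powers at N = 102, 0.91 and 0.876, are multiplied to give 80%. The sentence that does this begins "Assuming independence between PASI 75 and sPGA the power to show superiority of brodalumab compared to fumaric acid esters will be".

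The analysis treats the endpoints alike. Section 13.3.5, which covers both co-primaries, says "Subjects who drop-out of the trial before Week 24 (end of treatment visit) will be regarded as non-responders", and Section 13.3.11 says "Missing data for categorical endpoints will be imputed with non-responder imputation". Section 13.3.5 also makes success depend on superiority for both endpoints.

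**The concern.** Both co-primaries are measured in the same subjects at the same visit, so the same people drop out of both. A dropout allowance that roughly halves the PASI 75 rates cannot be absent for sPGA unless the sPGA rates already contain it. Section 13.1 does not say whether they do.

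The 80% is the only joint power given for the chosen 102 per arm, and Section 8.2 refers to Section 13.1 for the justification of the sample size. Because both endpoints must succeed, an error in the sPGA factor passes straight into the power of the trial. As written, a reader cannot tell what power the design has at its own planning values.

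**Working it through.** **Inputs (Section 13.1 and Panel 13).** N = 102 per arm; two-sided 5%; PASI 75 of 80% v 50% before dropout; dropout 40% (brodalumab, the upper limit given) and 50% (fumaric acid esters); sPGA 37.4% on fumaric acid esters. For brodalumab sPGA the text gives only a floor of 60%. I infer that exactly 60% was used, because it reproduces the panel.

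**Formula.** Continuity-corrected arcsine approximation to Fisher's test:

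power = Φ( √(2n) × [ arcsin√(p₁ − 1/(2n)) − arcsin√(p₂ + 1/(2n)) ] − 1.96 ), with √204 = 14.283.

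**Step 1: reproduce the plan.**
- PASI 75, 0.80 × 0.60 = 0.48 v 0.50 × 0.50 = 0.25: 14.283 × (0.7605 − 0.5292) − 1.96 = 1.343, power 0.910.
- sPGA, 0.60 v 0.374, undiscounted: 14.283 × (0.8811 − 0.6631) − 1.96 = 1.154, power 0.876.
- Product: 0.910 × 0.876 = 0.797, the stated 80%.

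The same formula returns all 16 cells of Panel 13 to three decimals, with PASI 75 at 48% v 25%, 30% and 35% and sPGA at 60% v 37.4%. The sPGA column therefore has no dropout step beyond whatever its source rates contain.

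**Step 2: read the sPGA rates as completer rates and apply the same dropout.**
- Brodalumab 0.60 × 0.60 = 0.360; fumaric acid esters 0.374 × 0.50 = 0.187.
- 14.283 × (0.6384 − 0.4534) − 1.96 = 0.682, power 0.752. Full enumeration of Fisher's test gives 0.755.
- Joint power under independence: 0.9103 × 0.7522 = 0.685.
- Joint power cannot exceed the smaller of the two powers, so under any correlation it is at most 0.752.

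**Step 3: range.** The text allows brodalumab sPGA above 60% and brodalumab dropout below 40%. The fumaric acid ester rates stay at 25% and 18.7%.

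| Brodalumab sPGA (completers) | Brodalumab dropout | PASI 75 power | sPGA power | Joint power |
|---|---|---|---|---|
| 60% | 40% | 0.910 | 0.752 | 0.685 |
| 65% | 40% | 0.910 | 0.870 | 0.792 |
| 70% | 40% | 0.910 | 0.941 | 0.857 |
| 80% | 40% | 0.910 | 0.992 | 0.903 |
| 60% | 38% | 0.942 | 0.805 | 0.758 |
| 60% | 36% | 0.964 | 0.850 | 0.820 |
| 60% | 35% | 0.972 | 0.870 | 0.846 |
| 60% | 30% | 0.994 | 0.941 | 0.935 |

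Joint power reaches 80% at a brodalumab sPGA rate of 65.5% (dropout 40%) or at brodalumab dropout of 36.7% (sPGA 60%).

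**Step 4: read the sPGA rates as already net of dropout.** The completer rate needed is the net rate divided by the share who stay.
- Brodalumab: 0.60/0.60 = 100% at 40% dropout; 0.60/0.65 = 92% at 35%; 0.60/0.70 = 86% at 30%; 0.60/0.75 = 80% at 25%.
- Fumaric acid esters: 0.374/0.50 = 74.8%, against 50% assumed for PASI 75 in the same completers.
- Net sPGA success would exceed net PASI 75 response in both arms (60% v 48% and 37.4% v 25%). The only brodalumab trial rates quoted, at Week 12 in Section 6.2.1, run the other way: "response rates of 86% for PASI 75, 80% for sPGA0/1".

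If the rates are net only of the dropout seen in their source trials, they still do not reflect the 40% and 50% assumed here.

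**The case against.** **The 68% is a corner value.** It takes brodalumab sPGA at its floor and brodalumab dropout at its ceiling. The only brodalumab sPGA rate in the documents is 80%, at Week 12 in one trial, and at 80% consistent handling gives joint power of 90%. This stands as a limit on what can be concluded. It does not rescue the printed 80%, which was computed at exactly 60% and 48%; moving off those values means restating the figure.

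**The planned test is Cochran-Mantel-Haenszel, not Fisher.** On an unstratified chi-square scale, the stated inputs give 0.933 × 0.904 = 0.84 and consistent dropout gives 0.933 × 0.796 = 0.74. The ceiling on joint power is then about 80% rather than 75.2%. This also stands: 68% is comparable with the plan's own Fisher-based 80% but is not the power of the planned analysis. The fall is of similar size on either scale.

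**The basis of the sPGA rates is unknown.** If both were already net of dropout, 0.91 × 0.876 would be correct as a product, and the brodalumab rate could be reconciled with dropout near 25%. But the 0.91 in that product uses 40% dropout, and the fumaric acid ester rate would still require 74.8% of completers to succeed. The two factors would still rest on conflicting assumptions.

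**The multiplication itself is correct.** Agreed. The fault lies in the inputs, and the tests, estimates and success rule are unaffected.

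**Conclusion.** The concern holds. The 80% does not follow from one consistent set of assumptions under either reading of the sPGA rates.

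If they are completer rates, the planning values (60% v 37.4%, dropout 40% and 50%, 102 per arm, Fisher's test) give sPGA power of about 75% instead of 87.6%. Joint power is then about 68% under independence and at most 75% under any correlation. If they are net rates, they conflict with the dropout behind the PASI 75 factor.

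This is not a finding that the trial is underpowered. In the scenarios tabulated, joint power runs from 68% to 94%, depending on how far brodalumab sPGA lies above 60% or dropout below 40%. The recomputed powers rest on the completer reading, which the documents neither confirm nor exclude, and the 60% is inferred from Panel 13. The mismatch of bases depends on neither the completer reading nor the choice of test.

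**What to change.** In Section 13.1:

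1. State for each sPGA rate whether it applies to completers or to all randomised subjects with dropouts counted as failures.
2. Recompute the sPGA column of Panel 13 on the all-randomised, non-responder basis used for PASI 75, and show the total response rate in its heading. If the rates are already on that basis, reconcile them with the 40% and 50% dropout and with the 48% and 25% PASI 75 totals.
3. Replace the single product by the resulting joint power and its range over the brodalumab sPGA rate, brodalumab dropout and the fumaric acid ester assumptions. With completer rates at 60% and 37.4% and dropout of 40% and 50%, the value is about 68%. Panel 13 already gives PASI 75 power at fumaric acid ester rates of 60% and 70%, so carrying these into the joint figure only adds to the reporting.

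The cost is one recalculation and a few sentences, with no new subjects and no change to the analysis.

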### 10.3 Treatment assignment

#### 10.3.1 Randomisation

Subjects who have been found to comply with all the inclusion criteria and not to violate any of the exclusion criteria will be randomised to receive treatment with either brodalumab or

fumaric acid esters. Treatment assignment will be pre-planned according to a computer generated randomisation schedule in a 1:1 ratio.

Randomisation will be with stratification by body weight (<100 kg or ≥100 kg) using an IWRS system.

Each investigator site will be supplied with sufficient IMPs for the trial on an ongoing basis controlled by the IWRS.

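### The 80% joint power assumes independent co-primaries, which the plan's own dropout figures rule out; the corrected figure turns on whether the sPGA rates already count dropouts as failures

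*Combined protocol and SAP*

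**What the plan says.** Section 13.1 fixes the sizing test: "The sample size is determined using Fisher's exact test for the two independent proportions under the assumption of a two-sided test of size 5" per cent. It takes "conservative estimates for the proportion of PASI 75 responders of 80% for brodalumab and between 50% and 70% for fumaric acid esters". It then discounts PASI 75 for dropout with non-responder imputation (NRI). Fumaric acid esters at 50% with 50% dropout become 25%. Brodalumab becomes 48%, with dropout described as less than 40%.

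For sPGA 0/1 the section gives 37.4% on fumaric acid esters, from a cited trial, and rates above 60% on brodalumab. It mentions no dropout discount for either.

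Panel 13 gives power at 102 per group of 0.910, 0.708 and 0.416 for PASI 75 (fumarate rates of 50%, 60% and 70% before dropout) and 0.876 for sPGA. The closing sentence begins "Assuming independence between PASI 75 and sPGA the power to show superiority of brodalumab compared to fumaric acid esters will be", and for 102 per arm it puts the product of 0.91 and 0.876 at 80%.

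Section 13.3.5 governs the analysis: "The differences in response rates between treatment groups will be analysed using the Cochran-Mantel-Haenszel test with stratification by weight group". It also says "Subjects who drop-out of the trial before Week 24 (end of treatment visit) will be regarded as non-responders", for both co-primaries, and it requires superiority on both for the trial to succeed.

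**The concern.** Success needs both endpoints, so joint power is the figure that matters, and 80% is the only one the plan gives. It comes from multiplying two marginal powers as if the endpoints were unrelated. Yet both are scored on the same subject at the same Week 24 visit, and a dropout fails both. With dropout of 40% to 50%, that shared failure alone ties them together. The two factors also belong to Fisher's exact test, not to the stratified Cochran-Mantel-Haenszel (CMH) test that will be run.

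Checking independence against the dropout figures raises a second issue. PASI 75 enters after a dropout discount and sPGA enters without one. The 80% therefore does not describe the planned decision rule under one consistent set of assumptions, and the direction of the error depends on what the sPGA rates mean.

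**Working it through.** **Inputs.** Two-sided 5%, 1:1 allocation, 102 per arm (Sections 13.1 and 10.3.1). PASI 75 totals: brodalumab 0.80 × 0.60 = 0.48; fumaric acid esters 0.50 × 0.50 = 0.25. sPGA: fumaric acid esters 0.374; brodalumab 0.60, inferred because it reproduces the Panel 13 column. Completion is 60% on brodalumab (implied by 48% = 0.80 × 0.60) and 50% on fumaric acid esters.

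**1. The plan's figure.** The Walters arcsine approximation to Fisher's test gives 0.9103 and 0.8757, matching Panel 13. The product 0.910 × 0.876 = 0.797 reproduces the stated 80%. Full enumeration of Fisher's test gives 0.912 and 0.890, with product 0.81.

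**2. Is independence possible?** Under NRI only completers can respond, so P(either) cannot exceed the completion rate c, and P(both) ≥ p1 + p2 − c.

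| Arm | P(both), independence | Least P(both) allowed | P(either), independence | Completers |
|---|---|---|---|---|
| Fumaric acid esters | 0.25 × 0.374 = 0.0935 | 0.25 + 0.374 − 0.50 = 0.124 | 0.624 − 0.0935 = 0.5305 | 0.50 |
| Brodalumab | 0.48 × 0.60 = 0.288 | 0.48 + 0.60 − 0.60 = 0.48 | 1.08 − 0.288 = 0.792 | 0.60 |

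Independence fails in both arms. For brodalumab it would need dropout of at most 1 − 0.792 = 20.8%, which no longer fits 48% as 80% of completers.

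**3. Joint power at the rates as used.** 400,000 simulated trials of paired outcomes. The CMH test has two weight strata, with 30% of subjects at or above 100 kg and equal rates across strata (both assumed).

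| Overlap of the two responses | Fisher | CMH |
|---|---|---|
| Independence (infeasible) | 0.811 | 0.839 |
| Least overlap allowed (0.48; 0.124) | 0.832 | 0.855 |
| Independent among completers (0.48; 0.187) | 0.842 | 0.863 |
| One response nested in the other (0.48; 0.25) | 0.853 | 0.873 |

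With independence among completers, moving the heavier stratum's share between 10% and 40% changes the CMH result by no more than 0.001.

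**4. What those rates imply for sPGA.** Among completers, sPGA success would be 0.60 / 0.60 = 100% on brodalumab, against 80% for PASI 75. On fumaric acid esters it would be 0.374 / 0.50 = 74.8%, against 50% for PASI 75. A brodalumab rate truly above 60% could not occur with 40% dropout.

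**5. Alternative reading (an assumption).** Suppose 60% and 37.4% are completer rates. NRI then gives 0.60 × 0.60 = 0.36 and 0.374 × 0.50 = 0.187. The sPGA power falls to 0.755 (Fisher) or 0.798 (CMH). Joint power:

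| Overlap | Fisher | CMH |
|---|---|---|
| Independent among completers | 0.712 | 0.761 |
| Nested | 0.745 | 0.789 |

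Overall independence still fails on brodalumab: 0.48 + 0.36 − 0.48 × 0.36 = 0.667 exceeds 0.60.

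**6. Other fumarate scenarios.** Joint power cannot exceed the weaker marginal. At fumarate PASI 75 rates of 60% and 70%, Panel 13 caps it at 0.708 and 0.416. The unstratified Mantel-Haenszel test gives caps of 0.762 and 0.484.

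**The case against.** The case against is substantial. The multiplication is correct and independence is declared openly. For given marginal rates, ignoring positive dependence understates joint power, so this simplification does not make the trial too small. Sizing on Fisher's test and analysing with CMH is common, errs on the safe side and is not a contradiction. CMH power also needs a weight split and stratum rates that the documents do not give. All of this stands, and it is why the point is minor.

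It does not rescue the sentence. A declared assumption that the same section's dropout figures exclude cannot support the only joint-power figure, and the choice of test moves that figure by two to three points.

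The strongest objection is that 0.855 to 0.873 rests on a boundary case, since every brodalumab completer must reach sPGA 0/1. That also stands, so the range should not be printed alone.

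A reader might infer more than the documents support:

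- *That the trial is underpowered because independence was assumed.* At the rates used, correcting the dependence raises the power.
- *That power is comfortably above 85%.* This needs undiscounted sPGA rates and the most favourable of the three fumarate scenarios.
- *That the sPGA rates certainly need discounting.* Section 13.1 does not say how dropouts were counted in its sPGA figures.
- *That a range free of dependence assumptions would settle it.* From the stated powers this runs from 0.91 + 0.876 − 1 = 0.786 to 0.876. Its lower end needs negative dependence, which shared dropout makes implausible, and it describes Fisher's test only.

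**Conclusion.** The point holds as a minor correction to the stated power. Independence is infeasible at the rates and dropout used in Section 13.1. Taken at face value, those rates give joint power at 102 per arm of 0.832 to 0.853 by Fisher's test and 0.855 to 0.873 by the planned CMH test, so 80% is understated on this ground alone.

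That result depends on brodalumab sPGA of 60% (inferred), brodalumab dropout of exactly 40%, equal rates across weight strata, and the 50% fumarate PASI 75 scenario. It is not reassurance. If the sPGA figures are completer rates, joint power is 0.712 to 0.745 (Fisher) or 0.761 to 0.789 (CMH) with non-negative dependence among completers, below 80% throughout. The documents do not say which reading applies, so neither set can be called the trial's power.

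**What to change.** In Section 13.1:

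1. Replace the independence sentence with joint power for the planned CMH test, using the dependence that shared dropouts impose. State the assumed weight split and stratum rates.
2. Apply the dropout and NRI discount to sPGA as to PASI 75, or state that 60% and 37.4% already count dropouts as failures. In the latter case, explain how 60% fits with 40% dropout. State the brodalumab sPGA rate explicitly.
3. Report joint power under both readings of the sPGA rates and for each of the three fumarate PASI 75 scenarios.
4. Do not replace this with bounds that ignore the dependence.

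The cost is a few sentences and a small table, with no change in sample size or conduct. The drawback is that the stated power will change and may look less favourable than 80%.
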